10.3. Treatment Period

10.3.1. Week 2/Visit 3

Week 2/Visit 3, will be conducted via telephone or videoconference. The following procedures and assessments will be completed:

- Concomitant medication use
- S-STS – The subject will be asked to complete the printed copy of the S-STS given to them at their Baseline Visit while communicating with the site staff. The staff will review the subject’s answers to the S-STS and recommend corrections, only where the

form has been completed incorrectly. The completed S-STS source document will be mailed back to the clinic or returned at the next study visit to be filed in the subject's chart and entered into the eCRF system.

- Adverse events
- Abuse and diversion assessment (MADDERS)
- Rescue medication appropriate use assessment by review of daily use entries in the handheld and by subject interview
- Study drug use and assessment of compliance by review of daily use entries in the handheld and by subject interview
- Compliance with entry into daily diary of pain intensity
- Subjects will be instructed to take one capsule of study drug by mouth once daily
- Subjects will be reminded not to exceed 3 g/day (one to two 500 mg tablets every 6 hours as needed) for pain related to fibromyalgia
- Subjects will be reminded on how to record their pain on the device and will also be reminded about appropriate expectations for their participation in a clinical study.

On each day until returning to the study site at Week 4/Visit4, subjects will record the following on the handheld device:

- At bedtime: average pain intensity and use of rescue medication during the past 24 hours.
- Upon waking: DSIS and confirm when study drug has been taken

- A subject may be asked to return to the clinic, per Investigator discretion, for additional study specific training or examination. Any unscheduled return to the clinic should be entered as an Unscheduled Visit into the eCRF and IRT systems.

10.3.2. Week 4/Visit 4 and Week 8/Visit 5

At Week 4/Visit 4 and Week 8/Visit 5, the following procedures and assessments will be performed/assessed:

- Concomitant medication use
- S-STS
- Adverse events
- Abuse and diversion assessment (MADDERS)
- Vital signs (blood pressure and pulse after sitting or lying supine for at least five minutes)
- Electrocardiogram after five minutes in supine position
- Blood samples for fasting (8 hours) serum chemistry and hematology
- Urine sample for urinalysis

- Urine pregnancy test, if clinically indicated for females of childbearing potential
- Urine drug test
- Rescue medication return, assessment of appropriate use by inventory of returned tablets, as well as by subject interview
- Study drug return and assessment of compliance by inventory of returned capsules, as well as by subject interview
- Compliance with entry into daily diary of pain intensity and rescue medication use
- PGI-C
- FIQR
- PROMIS_{FM} (sleep disturbance, fatigue profile and physical function)
- [REDACTED]
- Dispensing of study drug – Subjects will be instructed to take one capsule of study drug by mouth once daily
- Re-dispensing/dispensing of rescue medication – Subjects will be reminded not to exceed 3 g/day (one to two 500 mg tablets every 6 hours as needed) for pain related to fibromyalgia
- Subjects will be reminded on how to record their pain score on the device and will also be reminded about appropriate expectations for their participation in a clinical study and the importance of consistently and accurately reporting their pain intensity throughout the study. Review of these educational materials will be repeated for all subjects as refresher training or based on findings of an ongoing blinded data review (e.g., if pain score variability is increased on a subject or site level) via the aLearn[®] portal. On each day until returning to the study site at Week 8/Visit 5, subjects will record the following on the handheld device:
 - At bedtime: average pain intensity and use of rescue medication during the past 24 hours.
 - Upon waking: DSIS and confirm when study drug has been taken

10.3.3. Week 12/Visit 6/Early Termination Visit

At Week 12/Visit 6, or at the time of early termination from the study, the following procedures and assessments will be performed/assessed:

- Concomitant medication use
- S-STS
- Adverse events
- Abuse and diversion assessment (MADDERS)
- Vital signs (blood pressure and pulse after sitting or lying supine for at least five minutes)
- Electrocardiogram after five (5) minutes in supine position

- Body weight
- Brief physical examination
- Blood samples for fasting (8 hours) serum chemistry and hematology
- Urine sample for urinalysis
- Urine pregnancy test for females of childbearing potential
- Urine drug screen
- Compliance with entry into daily diary of pain intensity, rescue medication use and self-administration of study drug
- FIQR
- PGI-C
- PROMIS_{FM} (sleep disturbance, fatigue profile and physical function)
- [REDACTED]
- Study drug return and assessment of compliance by inventory of returned capsules, as well as by subject interview
- Rescue medication return and assessment of appropriate use by inventory of returned tablets, as well as by subject interview
- Study-issued handheld device and any other study related materials returned
- After completion of the study visits, the site will contact the subjects by telephone within 10 days to complete a safety follow-up call. The Investigator, at their discretion, may ask subject to return for an Unscheduled Visit for any safety concerns, abnormal laboratory or ECG findings.
- A final call will be made to the subject approximately 30 days after the final visit to assess for AE closure and any new SAEs.

11. STOPPING CRITERIA

Subjects will be withdrawn from the treatment period of the study if any of the following laboratory results and symptoms are observed.

- ALT or AST >8xULN – Discontinue subject treatment immediately.
- ALT or AST >5xULN
- ALT or AST >3xULN **and** (TBL >2xULN **or** INR >1.5)
Discontinue treatment if result is confirmed upon retest (to be done within 48 hours or as soon as feasible).
- ALT or AST >3xULN with the appearance of fatigue, nausea, vomiting, right upper quadrant pain or tenderness, fever, rash, and/or eosinophilia (>5%)
- ALT or AST >3xULN that persists for \geq 4 weeks

If an increase of serum aminotransferase of $>3\times\text{ULN}$ is identified, repeat testing within 48 to 72 hours of all four of the usual serum liver function test measures (ALT, AST, ALP, and TBL) should be conducted to confirm the abnormalities and to determine if they are increasing or decreasing.

12. STATISTICS

12.1. Sample Size Determination

The planned sample size of 300 subjects will provide approximately 80% power for statistical testing with an overall Type I error rate of 0.05.

12.2. Randomization

Pain scores reported by subjects during the Screening Period will be evaluated by the IRT system for raw score and for variability among scores after transmission of pain scores from the handheld devices to determine randomization eligibility. Subjects whose mean of the daily average pain intensity score during the preceding 7 days within the protocol-defined algorithm and whose compliance with daily diary completion is found to be adequate will be eligible for randomization. The absolute pain scores and variability among scores, as well as the actual percentage required for diary compliance, will be masked to investigators and subjects. Subject eligibility for randomization into the study based on these variables will be communicated to the investigator via the IRT system. The IRT system will notify the site if the subject is “Eligible” or “Not eligible.” No other information will be provided.

12.3. Statistical Analysis Plan

The planned statistical analysis methods, including procedures for accounting for missing, unused, and spurious data, will be described in more detail in the Statistical Analysis Plan, which will be finalized prior to study completion. Deviations from the original Statistical Analysis Plan will be described in the final clinical study report.

Descriptive statistics for categorical variables will include the number and percent of subjects with each characteristic. Percentages will be based on the number of subjects with nonmissing values. Descriptive statistics for ordinal and continuous variables will include the number of subjects with nonmissing values, mean, median, standard deviation, minimum value, and maximum value.

All relevant data collected in the eCRF will be shown for each subject in the individual subject data listings.

12.4. Analysis Populations

Safety analyses will be based on the Safety Population, defined as all subjects who receive at least one dose of study drug.

Efficacy analyses will be based on the modified Intent-to-Treat Population, defined as all subjects in the Safety Population with at least one postbaseline assessment of the pain intensity NRS.

12.5. Treatment Group Comparisons

The following treatment groups will be summarized in the statistical tables:

- NYX-2925 50 mg
- NYX-2925 100 mg
- Placebo

The following treatment group comparisons will be performed for efficacy:

- NYX-2925 50 mg versus placebo
- NYX-2925 100 mg versus placebo

12.6. Analyses of Efficacy

12.6.1. Primary Efficacy Analysis

The primary efficacy analysis will be performed based on the modified Intent-to-Treat population.

The primary efficacy endpoint is the change from baseline in the weekly mean of the daily NRS score assessing average pain intensity in the past 24 hours. The primary efficacy analysis will evaluate the treatment-policy estimand in the modified Intent-to-Treat population. The treatment-policy estimand combines the improvement (reduction) from Baseline in the weekly mean of the daily NRS score and not discontinuing treatment early due to an AE or lack of efficacy through Week 12.

The following four attributes describe the estimand that will be used to define the treatment effect of interest for the primary efficacy analysis:

1. Population = Subjects meeting the protocol-specified inclusion/exclusion criteria, who received at least one dose of study drug and who have at least one post-baseline assessment of the pain intensity NRS.
2. Subject-level outcome = Change from baseline in the weekly mean of the daily NRS score assessing average pain intensity in the past 24 hours
3. Intercurrent event handling = An intercurrent event is defined as discontinuation of study drug due to an AE or lack of efficacy prior to Week 12. For the analysis, baseline Observation Carried Forward (BOCF) imputation will be used to impute data for visits after a patient has discontinued randomized treatment due to either of these reasons (even if data is present).
4. Population-level summary measure = Difference in least squares mean change from baseline in the weekly mean of the daily NRS score at Week 12, comparing each dose of NYX-2925 to placebo.

Any missing data at Week 12 that are not preceded by an intercurrent event (i.e., discontinuation of study drug due to AE or lack of efficacy) will remain as missing.

For the primary efficacy endpoint, the daily pain intensity NRS score from the handheld device will be averaged for baseline after randomization. Change from baseline will be assessed for

treatment group difference using a mixed model for repeated measures (MMRM) with factors for study site, treatment, week, treatment by week interaction, and including the baseline value of the response variable as a covariate. Line plots displaying the mean weekly NRS scores from Weeks 1 through 12 for each treatment group will be generated. In these plots, the horizontal axis will reflect the study week and the vertical axis will reflect the average pain score.

12.6.2. Sensitivity Analysis

As a sensitivity analysis for the primary efficacy endpoint, an analysis of covariance (ANCOVA) model will be used to assess treatment differences. The model will include factors for study site and treatment and include the baseline value of the response variable as a covariate.

Sensitivity analyses will be performed on the primary endpoint, evaluating the impact of the missing at random (MAR) assumption for missing data. Multiple imputation (MI) techniques based on Pattern Mixture Models (PMM) will be applied as the first sensitivity analysis. This methodology will structure data based on a missingness pattern having a monotone structure. An MI analysis with missing not at random (MNAR) assumption will be applied as the second sensitivity analysis. Placebo group based imputation will be used (i.e. the trajectories of the subjects with missing data on NYX-2925 are assumed to follow the placebo group after discontinuation).

If the primary efficacy analysis significantly favors one or both doses of NYX-2925, a tipping point sensitivity analysis for the primary efficacy endpoint will be conducted. In this analysis, the assumption will be that that data in the NYX-2925 groups are not missing at random. A tipping point based assumption will be used, i.e. the trajectories of the subjects in each of the NYX-2925 groups after withdrawal are assumed to be worse than placebo by an amount of delta.

Successively harsher deltas will be imposed on the subjects in the NYX-2925 groups, starting with a mean weekly NRS score increment (increase) of 0.5 points. The delta will be further increased in steps of 0.5 points (i.e., 1.0, 1.5, 2.0) until the statistical significance is lost, i.e. until the p-value becomes >0.05 .

[figure not shown]
12.6.3. Secondary Efficacy Endpoints

The following secondary endpoints will be analyzed:

- Percentage of subjects “much improved” or “very much improved” on the Patient Global Impression of Change (PGI-C) at Week 12
- Change from baseline in the weekly mean of the Daily Sleep Interference Scale (DSIS) scores at Week 12
- Percentage of subjects achieving $\geq 30\%$ reduction from baseline in the weekly mean NRS average pain intensity at Week 12
- Percentage of subjects achieving $\geq 50\%$ reduction from baseline in the weekly mean NRS average pain intensity related to fibromyalgia at Week 12
- Change from baseline to Week 12 in the Fibromyalgia Impact Questionnaire – Revised (FIQR) score
- Change from baseline to Week 12 in the Patient Reported Outcomes Measurement Information System – Fibromyalgia (PROMIS_{FM}) sleep disturbance score

- Change from baseline to Week 12 in the Patient Reported Outcomes Measurement Information System – Fibromyalgia (PROMIS_{FM}) fatigue profile score
- Change from baseline to Week 12 in the Patient Reported Outcomes Measurement Information System – Fibromyalgia (PROMIS_{FM}) physical function score
- Cumulative response (percent reduction from baseline) in the weekly mean NRS average pain intensity at Week 12
- Use of rescue medication, including the proportion of subjects using rescue medication, the frequency and amount used
- Change from baseline in the weekly mean of the daily Numerical Rating Scale (NRS) at each week from Week 1 through Week 12

12.6.4. Other Efficacy Analyses

12.6.5. Multiple Comparisons

The primary efficacy endpoint and primary statistical analysis are protocol specified.

The primary efficacy endpoint and other selected efficacy endpoints will be tested (using MMRM as described above) to preserve the overall Type I error rate.

There will be no other adjustments for multiple comparisons.

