The use of rescue medication will be summarized descriptively. The percentage of subjects achieving $\geq 30\%$ reduction in the mean NRS average pain intensity, the percentage of subjects achieving $\geq 50\%$ reduction in the mean NRS average pain intensity and sustainability of pain reduction in the mean NRS average pain intensity will be summarized.

The number of days to the first $\geq 30\%$ reduction and number of days to first $\geq 50\%$ reduction in the mean NRS average pain intensity will be assessed for treatment group differences with the log-rank test.

Adverse events will be categorized by system organ class and preferred term with the Medical Dictionary for Regulatory Activities (MedDRA). Summary tables for treatment-emergent adverse events (TEAEs) will include number and percent of subjects experiencing TEAEs by system organ class and preferred term.

Mean change in clinical laboratory and vital signs from baseline will be summarized descriptively. Clinical laboratory results considered clinically important by the Investigator will be identified.

Subjects with suicidal ideation or behavior will be identified with the S-STS.

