6.11 Efficacy Analyses

All statistical tests will be performed using a one-tailed 5% overall significance level as primary analysis. All comparisons between treatments will be reported with one-sided 95% confidence intervals (CI). All analyses will be performed independently on the treatment groups.

All statistical tests will be repeated using a two-sided 5% overall significance level, unless otherwise stated. All comparisons between treatments will be also reported with two-sided 95% CI.

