6.11.4 Secondary Endpoints

All secondary endpoints will be analyzed by one-sided testing using the mITT population. The two-sided testing will be also performed for all secondary endpoints, unless otherwise stated.

6.11.4.1 Percentage of Subjects “much improved” or “very much improved” on the Patient Global Impression of Change (PGI-C) at Week 12

Analysis will utilize the one-sided Chi-square test to compare the risk between treatment groups, using the following SAS code:

```
PROC FREQ DATA= DATAIN ORDER=DATA;
TABLES TREATMENT*RESP / riskdiff (column=2 method=wald equal var=null)
ALPHA=0.10;
ODS OUTPUT PDIFFCLS = DIFF1 PDIFFTEST = PVAL1;
RUN;
```

The number and percentage of subjects ‘much improved’ or ‘very much improved’ by treatment at each visit will be presented. The risk difference for NYX-2925 50 mg vs placebo and NYX-2925 100 mg vs placebo, the corresponding 1-sided 95% CI and 1-sided p-value for the Chi Square statistic will also be provided by visit. The lower limit of the 95% one-sided CI for the risk difference will be extracted as the lower limit of the 90% two-sided CI using the ALPHA=0.10 option with the upper limit being set to positive infinity. 2-sided Chi Square test will be performed as well with the risk difference, corresponding 2-sided 95% CI and 2-sided p-value.

Summary statistics for the PGI-C as a continuous score will also be provided by treatment group at each visit. Scores will be analyzed using the same REML-based MMRM as in the primary analysis, except with the exclusion of a baseline covariate.

The analysis will be repeated for Week 4 and Week 8. Observed scores will also be presented by treatment group. The LS means, corresponding SEs, and 95% CIs for each treatment group will be presented at each week along with the LS mean difference, corresponding SE, 1-sided 95% CI and 1-sided p-value.

A listing of all PGI-C scores will also be provided.

The analysis will be repeated for Weeks 4, 8, and 12 and observed value of PGI-C, and number and percentage of subjects ‘much improved’ or ‘very much improved’ on PGI-C will be presented.

6.11.4.2 Change from baseline in the weekly mean of the Daily Sleep Interference Scale (DSIS) scores at Week 12

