6.11.5 Other Efficacy Endpoints

6.11.6 Multiplicity

No multiplicity adjustment will be made on the secondary and other efficacy endpoints.

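### The protocol says that selected efficacy endpoints are tested so as to preserve the overall Type I error, but names no procedure, and the SAP tests every secondary endpoint unadjusted at both doses

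*Protocol*

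**What the plan says.** Protocol 12.6.5 contains two relevant sentences. The first says that the primary efficacy endpoint and "other selected efficacy endpoints will be tested (using MMRM as described above) to preserve the overall Type I error rate". The second reads: "There will be no other adjustments for multiple comparisons". The word *other* in the second implies that the first was meant as an adjustment. Protocol 12.1 gives the rate in question: "The planned sample size of 300 subjects will provide approximately 80% power for statistical testing with an overall Type I error rate of 0.05".

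SAP 6.11.6 consists of one sentence: "No multiplicity adjustment will be made on the secondary and other efficacy endpoints". SAP 6.11 sets the level: "All statistical tests will be performed using a one-tailed 5% overall significance level as primary analysis". It also says that the treatment groups are analysed independently and that the tests are repeated two-sided. SAP 6.11.4 adds: "All secondary endpoints will be analyzed by one-sided testing using the mITT population".

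On which endpoints are tested at all, the protocol is not uniform. The Synopsis says that PGI-C and the 30% and 50% responder percentages will be summarized, and on rescue use: "The use of rescue medication will be summarized descriptively". Protocol 12.6.3 lists the same endpoints among the secondary endpoints to be analyzed. The SAP tests them all.

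**The concern.** The protocol claims a property that the analysis plan does not have. An MMRM handles repeated measures within one endpoint; it does nothing about the number of endpoints or doses tested. The SAP supplies no procedure that would fill the gap. No secondary test depends on the primary result; the only analysis in the readable efficacy sections that does is the tipping-point analysis (SAP 6.11.3.2).

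The risk is in reporting. Someone relying on Protocol 12.6.5 could present a secondary p<0.05 as error-controlled, even for a dose that fails on the primary. SAP Section 9, the place for departures from the protocol, lists in readable text only the move to one-sided tests, the PROMIS naming and the Week 12 wording of the primary endpoint. The post-lock addendum does not mention multiplicity.

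**Working it through.** **1. The plan's own figure.** SAP Section 4: 85 per arm, difference 0.73, SD 1.7, one-sided 0.05, no correction for multiple testing.

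- SE = 1.7 × √(2/85) = 0.261, and 0.73/0.261 = 2.80.
- Power = Φ(2.80 − 1.645) = 87.6%, which reproduces the stated 88%.

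**2. How many tests.** Two counts are useful.

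- *Narrow count, k = 5 per dose.* Protocol 12.6.5 refers to endpoints tested by MMRM. Besides weekly NRS, the named secondary endpoints that the Synopsis analyses in that way are DSIS, FIQR and the three PROMIS scores (sleep disturbance, fatigue, physical function).
- *Wide count, k = 15 per dose.* End-of-study tests in SAP 6.11.4: PGI-C response, PGI-C score, DSIS, 30% response, 50% response, FIQR, sleep disturbance, four fatigue subscores, physical function, cumulative response, rescue proportion and rescue dose (7 + 4 + 4 = 15).

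**3. Model when neither dose works on any endpoint.** Each test is one-sided at 0.05 (critical value 1.645).

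- With equal arms and one shared placebo group, the two dose statistics for one endpoint have correlation (1/n)/(2/n) = 0.5.
- Endpoints are given a common correlation ρ. This is my assumption, with range 0.3 to 0.7.
- P(at least one false positive) = 1 − E[Φ₂(u₁, u₂; 0.5)^k], where u_d = (1.645 − √ρ·G_d)/√(1 − ρ). Here G₁ and G₂ are standard normal with correlation 0.5, and Φ₂ is the bivariate normal distribution function.

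| Tests per dose | ρ = 0.3 | ρ = 0.5 | ρ = 0.7 | All tests independent: 1 − 0.95^(2k) |
|---|---|---|---|---|
| 5 | 0.31 | 0.27 | 0.22 | 0.40 |
| 15 | 0.56 | 0.45 | 0.34 | 0.79 |

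Simulation of the same model agrees to within about 0.01.

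**4. What conditioning on the primary would achieve.** With k = 1, the formula gives the chance that at least one dose falsely succeeds on the primary.

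- Two tests at one-sided 0.05 each: 8.8%.
- Two tests at one-sided 0.025 each: 4.5%.

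Making secondary tests depend on two unadjusted 5% primary tests would therefore not bring the overall rate to 5%. A fixed split between doses would.

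**The case against.** The strongest reply is that this is a Phase 2 trial, that Protocol 12.3 leaves analysis detail to the SAP, and that SAP 6.11.6 says openly that secondary endpoints are unadjusted. Unadjusted secondary tests, declared as such, are a defensible choice, and the protocol named no method that the SAP could be said to have abandoned. That stands as far as it goes. The defect is that two documents in force say opposite things about error control, and the readable record of changes is silent.

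A reader might also infer several stronger things that the documents do not support:

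- *That the protocol promised control over the secondary endpoints as such.* It says other selected efficacy endpoints. There is also a separate category of other efficacy endpoints whose contents are not visible. Which were meant cannot be settled, but SAP 6.11.6 disclaims adjustment for both categories, so the conflict remains either way.
- *That the protocol limited PGI-C, responder and rescue endpoints to description.* The Synopsis wording points that way, but Protocol 12.6.3 says they will be analyzed.
- *That the change was left out of SAP Section 9.* One item there is redacted, so this can be said only of the readable text.
- *That the whole 34% to 56% breaches the protocol's statement.* That statement refers to MMRM tests. PGI-C response, the responder rates, cumulative response and rescue proportion are not MMRM tests, and the PGI-C score is not a listed endpoint. The five-endpoint figure is the fairer measure.

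**Conclusion.** The point holds. Protocol 12.6.5 states Type I control for an unspecified set of endpoints, through a method that cannot provide it, and the SAP makes no adjustment. If neither dose works, the chance of at least one nominally significant secondary result is about 22% to 31% on the narrow count and about 34% to 56% on the wide one, against a stated overall rate of 5%.

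These sizes rest on assumed equal endpoint correlations of 0.3 to 0.7, one test per item and a shared placebo arm with equal groups. Equal correlation is a simplification: the 30%, 50% and cumulative responses all come from the same Week 12 NRS score. The figures show scale and are not precise. The textual conflict does not depend on them.

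**What to change.** **If set before unblinding.** In SAP 6.11.6, name a short fixed sequence of secondary endpoints for each dose. Test it only after that dose succeeds on the primary, at that dose's share of a fixed alpha split between the two doses, and stop at the first failure. Label all other secondary p-values nominal. Ordering the secondary tests costs no primary power, but the split does: at one-sided 0.025 per dose, power is Φ(2.80 − 1.96) = 79.9%, against 87.6% unsplit.

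**If the study is already unblinded.** This is the position stated in the SAP addendum. Add no confirmatory sequence, because an order chosen now would be post hoc. Label all secondary and other p-values nominal, remove or correct the Type I claim in Protocol 12.6.5, and record the change in SAP Section 9 and the study report. Protocol 12.3 already requires SAP deviations to be described in that report.

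The second route costs only wording. On either route the small downside is that secondary results outside a prespecified sequence carry no error-controlled claim; on the second route that means all of them.
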